4. SUBJECT REGISTRATION

All subjects must be registered through HCRN's electronic data capture (EDC) system. A subject is considered registered when an "On Study" date is entered into the EDC system. Subjects must be registered prior to starting protocol therapy.

5. TREATMENT PLAN

5.1 Pre-medication and Hydration

There are no pre-medications for sylvatron or pembrolizumab

5.2 Pembrolizumab and Sylvatron Administration

Each cycle = 21 days or 3 weeks. Sylvatron will be administered at 200mcg subcutaneously every week for up to 12 weeks (3 weeks as single agent, and 9 weeks in combination of pembrolizumab) starting Cycle 1 Day 1. The dose of sylvatron may be reduced to 120mcg weekly, or 60mcg weekly if patients experience unacceptable toxicities at the higher dose levels. Patients will be premedicated with acetaminophen 500 to 1000 mg orally 30 minutes prior to the first dose of sylvatron and as needed for subsequent doses. Injection sites will be rotated. During the Cycle 1 Day 1 visit, subjects will be provided education on how to manage sylvatron injections at home.

Pembrolizumab will be administered intravenously as a 30 minute infusion at a dose of 200 mg every 3 weeks starting Week 4 (Cycle 2 Day 1). **All trial treatments will be administered on an outpatient basis.** On the days that sylvatron and pembrolizumab are given together, sylvatron should be administered prior to the pembrolizumab infusion.

Sites should make every effort to target infusion timing to be as close to 30 minutes as possible. However, given the variability of infusion pumps from site to site, a window of -5 minutes and +10 minutes is permitted (i.e., infusion time is 30 minutes: -5 min/+10 min). The Pharmacy Manual contains specific instructions for the preparation of the pembrolizumab infusion fluid and administration of infusion solution.

With concerns about toxicity while using long-term sylvatron, if no additional benefit is seen beyond 12 weeks of treatment on top of that expected from pembrolizumab alone, patients will discontinue sylvatron treatment after they have received 12 weeks of this therapy (3 weeks as single agent and 9 weeks in combination with pembrolizumab). Pembrolizumab should be continued in the absence of unacceptable toxicity (based on CTCAE v4) until disease progression-based on RECIST 1.1. In patients who had responded to the combination therapy, when patient shows disease progression while on single agent pembrolizumab treatment, sylvatron may be resumed at the discretion of the site investigator after discussion with the sponsor-investigator.

Medication Administration (Cycle = 21 days or 3 weeks)

Drug	Dose	Route	Schedule	Regimen Treatment Period	Cycle
Sylatron	200mcg	Subcutaneous injection	Q1W starting C1D1	Day 1, 8 and 15 of each cycle (weekly)	21 days
Pembrolizumab	200mg	Intravenous Infusion (IV) over 30 minutes	Q3W starting C2D1	Day 1 of each cycle	21 days

Dosing interruptions are permitted in the case of medical/surgical events or logistical reasons not related to study therapy (e.g., elective surgery, unrelated medical events, patient vacation, and/or holidays). Subjects should be placed back on study therapy within 3 weeks of the scheduled interruption, unless otherwise discussed with the sponsor-investigator. The reason for interruption should be documented in the subject's chart and electronic case report forms (eCRFs).

5.3 Treatment Beyond Radiological Disease Progression with Pembrolizumab

Accumulating clinical evidence indicates that some subjects treated with immune system stimulating agents may develop disease progression by conventional response criteria before demonstrating clinical objective responses and/or stable disease. This phenomenon was observed in the Phase I study of nivolumab, CA209003. Two hypotheses explain this phenomenon. First, enhanced inflammation within tumors could lead to an increase in tumor size, which would appear as enlarged index lesions and as newly visible small non-index lesions. Over time, both the malignant and inflammatory portions of the mass may then decrease leading to overt signs of clinical improvement. Alternatively, in some individuals, the kinetics of tumor growth may initially outpace anti-tumor immune activity. With sufficient time, the anti-tumor activity will dominate and become clinically apparent. Therefore, subjects will be allowed to continue study therapy after an initial investigator-assessed RECIST 1.1 defined progression as long as they meet the following criteria:

1. Site investigator assessed clinical benefit, and
2. Subject is tolerating treatment.

These criteria aim to ensure the risk/benefit for continuing treatment will continue to favor the subjects. The assessment of clinical benefit should take into account whether the subject is clinically deteriorating and unlikely to receive further benefit from continued treatment. Palliative radiotherapy or surgical resection of isolated lesions is permitted in these subjects and will not preclude the continued treatment with pembrolizumab.

All decisions to continue treatment beyond initial progression must be discussed with the sponsor-investigator and documented in the study records. Subjects should discontinue study therapy upon further evidence of further progression, defined as an additional 10% or greater increase in tumor burden volume from time of initial progression (including all target lesions and new measurable lesions). New lesions are considered measurable at the time of initial progression if the longest diameter is at least 10 mm (except for pathological lymph nodes, which must have a short axis of at least 15 mm). Any new lesion considered non-measurable at the time of initial progression may become measurable and therefore included in the tumor

burden measurement if the longest diameter increases to at least 10 mm (except for pathological lymph nodes, which must have an increase in short axis to at least 15 mm).

For statistical analyses that include the site investigator-assessed progression date, subjects who continue treatment beyond initial site investigator-assessed, RECIST 1.1-defined progression will be considered to have site investigator-assessed progressive disease at the time of the initial progression event.

5.4 Discontinuation of Pembrolizumab after CR

Discontinuation of treatment may be considered for subjects who have attained a confirmed CR that have been treated for at least 24 weeks with pembrolizumab and had at least two treatments with pembrolizumab beyond the date when the initial CR was declared. Subjects who then experience radiographic disease progression may be eligible for up to one year of additional treatment with pembrolizumab at the discretion of the site investigator if no cancer treatment was administered since the last dose of pembrolizumab, the subject meets the safety parameters listed in the Inclusion/Exclusion criteria, and the trial is open. Subjects will resume therapy at the same dose and schedule at the time of initial discontinuation.

5.5 Concomitant Medications

Medications or vaccinations specifically prohibited in the exclusion criteria are not allowed during the ongoing trial. If there is a clinical indication for one of these or other medications or vaccinations specifically prohibited during the trial, discontinuation from trial therapy or vaccination may be required. The site investigator should discuss any questions regarding this with the sponsor-investigator. The final decision on any supportive therapy or vaccination rests with the site investigator and/or the subject's primary physician.

5.5.1 Allowed Concomitant Medications

All treatments that the site investigator considers necessary for a subject's welfare may be administered at the discretion of the site investigator in keeping with the community standards of medical care. All concomitant medication will be recorded on the case report form (eCRF) including all prescription, over-the-counter (OTC), herbal supplements, and IV medications and fluids. If changes occur during the trial period, documentation of drug dosage, frequency, route, and date may also be included on the eCRF.

All concomitant medications received within 28 days before the first dose of trial treatment and 30 days after the last dose of trial treatment should be recorded. Concomitant medications administered after 30 days after the last dose of trial treatment should be recorded for SAEs and ECIs.

5.5.2 Prohibited Concomitant Medications

Subjects are prohibited from receiving the following therapies during the Screening and Treatment Phase (including retreatment for post-complete response relapse) of this trial:

- Antineoplastic systemic chemotherapy or biological therapy
- Immunotherapy not specified in this protocol
- Chemotherapy not specified in this protocol
- Investigational agents other than pembrolizumab
- Radiation therapy
 - **NOTE:** Radiation therapy to a symptomatic solitary lesion or to the brain may be allowed at the site investigator's discretion.
- Live vaccines within 30 days prior to the first dose of trial treatment and while participating in the trial. Examples of live vaccines include, but are not limited to, the following: measles, mumps, rubella, varicella/zoster, yellow fever, rabies, BCG, and typhoid vaccine.
- Systemic glucocorticoids for any purpose other than to modulate symptoms from an event of clinical interest of suspected immunologic etiology. The use of physiologic doses of corticosteroids may be approved after consultation with the Sponsor.

Subjects who, in the assessment by the site investigator, require the use of any of the aforementioned treatments for clinical management should be removed from the trial. Subjects may receive other medications that the investigator deems to be medically necessary. The Exclusion Criteria describes other medications which are prohibited in this trial. There are no prohibited therapies during the Post-Treatment Follow-up Phase.

5.6 Supportive Care

Subjects should receive appropriate supportive care measures as deemed necessary by the site investigator. Suggested supportive care measures for the management of adverse events with potential immunologic etiology are outlined below. Where appropriate, these guidelines include the use of oral or intravenous treatment with corticosteroids as well as additional anti-inflammatory agents if symptoms do not improve with administration of corticosteroids. Note that several courses of steroid tapering may be necessary as symptoms may worsen when the steroid dose is decreased. For each disorder, attempts should be made to rule out other causes such as metastatic disease or bacterial or viral infection, which might require additional supportive care. The treatment guidelines are intended to be applied when the site investigator determines the events to be related to pembrolizumab.

It may be necessary to perform conditional procedures such as bronchoscopy, endoscopy, or skin photography as part of evaluation of the event.

Pneumonitis

- For **Grade 2 events**, treat with systemic corticosteroids. When symptoms improve to Grade 1 or less, steroid taper should be started and continued over no less than 4 weeks.
- For **Grade 3-4 events**, immediately treat with intravenous steroids. Administer additional anti-inflammatory measures, as needed.
- Add prophylactic antibiotics for opportunistic infections in the case of prolonged steroid administration.

Diarrhea/Colitis

Subjects should be carefully monitored for signs and symptoms of enterocolitis (such as diarrhea, abdominal pain, blood or mucus in stool, with or without fever) and of bowel perforation (such as peritoneal signs and ileus).

- All subjects who experience diarrhea/colitis should be advised to drink liberal quantities of clear fluids. If sufficient oral fluid intake is not feasible, fluid and electrolytes should be substituted via IV infusion. For Grade 2 or higher diarrhea, consider GI consultation and endoscopy to confirm or rule out colitis.
- For **Grade 2 diarrhea/colitis** that persists greater than 3 days, administer oral corticosteroids.
- For **Grade 3 or 4 diarrhea/colitis** that persists > 1 week, treat with intravenous steroids followed by high dose oral steroids.
- When symptoms improve to Grade 1 or less, steroid taper should be started and continued over no less than 4 weeks.

Type 1 diabetes mellitus (if new onset, including diabetic ketoacidosis [DKA]) or \geq Grade 3 Hyperglycemia, if associated with ketosis (ketonuria) or metabolic acidosis (DKA)

- For **T1DM** or **Grade 3-4 Hyperglycemia**
 - Insulin replacement therapy is recommended for Type I diabetes mellitus and for Grade 3-4 hyperglycemia associated with metabolic acidosis or ketonuria.
 - Evaluate patients with serum glucose and a metabolic panel, urine ketones, glycosylated hemoglobin, and C-peptide.

Hypophysitis

- For **Grade 2** events, treat with corticosteroids. When symptoms improve to Grade 1 or less, steroid taper should be started and continued over no less than 4 weeks. Replacement of appropriate hormones may be required as the steroid dose is tapered.
- For **Grade 3-4** events, treat with an initial dose of IV corticosteroids followed by oral corticosteroids. When symptoms improve to Grade 1 or less, steroid taper should be started and continued over no less than 4 weeks. Replacement of appropriate hormones may be required as the steroid dose is tapered.

Hyperthyroidism or Hypothyroidism

Thyroid disorders can occur at any time during treatment. Monitor patients for changes in thyroid function (at the start of treatment, periodically during treatment, and as indicated based on clinical evaluation) and for clinical signs and symptoms of thyroid disorders.

- **Grade 2** hyperthyroidism events (and **Grade 2-4** hypothyroidism):
 - In hyperthyroidism, non-selective beta-blockers (e.g. propranolol) are suggested as initial therapy.
 - In hypothyroidism, thyroid hormone replacement therapy, with levothyroxine or liothyronine, is indicated per standard of care.
- **Grade 3-4** hyperthyroidism
 - Treat with an initial dose of IV corticosteroid followed by oral corticosteroids. When symptoms improve to Grade 1 or less, steroid taper should be started and continued over no less than 4 weeks. Replacement of appropriate hormones may be required as the steroid dose is tapered.

Hepatic

- For **Grade 2** events, monitor liver function tests more frequently until returned to baseline values (consider weekly).
 - Treat with IV or oral corticosteroids
- For **Grade 3-4** events, treat with intravenous corticosteroids for 24 to 48 hours.
- When symptoms improve to Grade 1 or less, a steroid taper should be started and continued over no less than 4 weeks.

Renal Failure or Nephritis

- For **Grade 2** events, treat with corticosteroids.
- For **Grade 3-4** events, treat with systemic corticosteroids.
- When symptoms improve to Grade 1 or less, steroid taper should be started and continued over no less than 4 weeks.

Management of Infusion Reactions Signs and symptoms usually develop during or shortly after drug infusion and generally resolve completely within 24 hours of completion of infusion. Table 2 below shows treatment guidelines for subjects who experience an infusion reaction associated with administration of pembrolizumab.

Table 2: Infusion Reaction Treatment Guidelines

NCI CTCAE Grade	Treatment	Premedication at subsequent dosing
Grade 1 Mild reaction; infusion interruption not indicated; intervention not indicated	Increase monitoring of vital signs as medically indicated until the subject is deemed medically stable in the opinion of the investigator.	None
Grade 2 Requires infusion interruption but responds promptly to symptomatic treatment (e.g., antihistamines, NSAIDS, narcotics, IV fluids); prophylactic medications indicated for <=24 hr	
Stop Infusion and monitor symptoms.
 
Additional appropriate medical therapy may include but is not limited to: IV fluids, Antihistamines, NSAIDS Acetaminophen, Narcotics
 
Increase monitoring of vital signs as medically indicated until the subject is deemed medically stable in the opinion of the investigator.
 
If symptoms resolve within one hour of stopping drug infusion, the infusion may be restarted at 50% of the original infusion rate (e.g., from 100 mL/hr to 50 mL/hr). Otherwise dosing will be held until symptoms resolve and the subject should be premedicated for the next scheduled dose.
 
Subjects who develop Grade 2 toxicity despite adequate premedication should be permanently discontinued from further trial treatment administration.
	
Subject may be premedicated 1.5 hr (\pm 30 minutes) prior to infusion of pembrolizumab (MK-3475) with:
 
Diphenhydramine 50 mg po (or equivalent dose of antihistamine).
 
Acetaminophen 500-1000 mg po (or equivalent dose of antipyretic).

NCI CTCAE Grade	Treatment	Premedication at subsequent dosing

Grades 3 or 4
 
Grade 3: Prolonged (i.e., not rapidly responsive to symptomatic medication and/or brief interruption of infusion); recurrence of symptoms following initial improvement; hospitalization indicated for other clinical sequelae (e.g., renal impairment, pulmonary infiltrates)
 
Grade 4: Life-threatening; pressor or ventilatory support indicated
	
Stop Infusion. Additional appropriate medical therapy may include but is not limited to:
 
 IV fluids Antihistamines NSAIDS Acetaminophen Narcotics Oxygen Pressors Corticosteroids Epinephrine 
Increase monitoring of vital signs as medically indicated until the subject is deemed medically stable in the opinion of the investigator. Hospitalization may be indicated.
 
Subject is permanently discontinued from further trial treatment administration.
	
No subsequent dosing

Appropriate resuscitation equipment should be available in the room and a physician readily available during the period of drug administration.
		

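### Section 5.6 ties IV steroids for Grade 3-4 diarrhea/colitis to more than a week's persistence, longer than at Grade 2; Table 3 states no wait and nothing says which governs

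*Combined protocol and SAP*

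**What the plan says.** Section 5.6 (Supportive Care) introduces its content this way: "Suggested supportive care measures for the management of adverse events with potential immunologic etiology are outlined below". It then sets the scope: "The treatment guidelines are intended to be applied when the site investigator determines the events to be related to pembrolizumab".

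Under Diarrhea/Colitis it gives these instructions:

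- **Grade 2:** oral steroids for an event "that persists greater than 3 days, administer oral corticosteroids".
- **Grade 3 or 4:** IV steroids for an event "that persists > 1 week, treat with intravenous steroids followed by high dose oral steroids".
- **Work-up from Grade 2 upward:** "consider GI consultation and endoscopy to confirm or rule out colitis", with no persistence condition.

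Section 6.1, Table 3, covers the same toxicity in a column on managing immune-related events with corticosteroids. Its entry for Grade 2 or 3 diarrhea/colitis is corticosteroid at a starting dose of 1-2 mg/kg prednisone-equivalent, then a taper. General instruction 3 of that table puts IV corticosteroid before oral steroid for severe and life-threatening immune-related events. Neither states a waiting period. For the drug itself, Table 3 withholds pembrolizumab at Grade 2 or 3 and stops it permanently at Grade 4.

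**The concern.** Two features of the Grade 3-4 bullet look wrong. First, the triggers run against severity: the worse event must last longer before a steroid instruction applies, and no reason is given. Second, Table 3 addresses steroid treatment of the same event without any such condition, and the protocol does not say which section a site should follow.

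What is at stake is patient safety. Section 5.6 itself asks sites to watch for bowel perforation, and Table 3 treats Grade 4 as a reason to stop the drug for good. A site that reads 5.6 literally could hold back IV steroids in a patient with severe immune-related colitis. Sites in this multicenter trial could also act differently from one another, depending on which section they consult.

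**Working it through.** No sample size, power or error rate is involved, and the plan gives no figure to reproduce. The check compares texts and makes one count.

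**1. Triggers by grade in Section 5.6**

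| Event | Stated trigger | Steroid |
|---|---|---|
| Grade 2 diarrhea/colitis | more than 3 days | oral |
| Grade 3 or 4 diarrhea/colitis | more than 1 week (7 days) | IV, then high-dose oral |

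The stated trigger at the higher grade is 7 − 3 = 4 days longer. On day 5, for example, a continuing Grade 2 event has passed its trigger (5 > 3), while a continuing Grade 3 or 4 event has not (5 < 7). Read literally, 5.6 then gives a steroid instruction for the milder event and none for the more severe one.

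**2. The same event in Table 3**

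| Item | Section 5.6 | Section 6.1, Table 3 |
|---|---|---|
| Steroids at Grade 3 | IV after more than 1 week | 1-2 mg/kg prednisone-equivalent, no persistence condition; IV first for severe events (instruction 3) |
| Steroids at Grade 4 | IV after more than 1 week | IV first for life-threatening events (instruction 3), no persistence condition |
| Fluids advice | given | same advice |
| GI consultation and endoscopy | consider from Grade 2 | consider from Grade 2 |

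In the text available, Table 3's steroid entry sits against Grade 2 or 3 and the Grade 4 cell is blank, which may be a merged cell. Nothing turns on this, because instruction 3 covers life-threatening events. The overlap in fluids and endoscopy advice shows that the two sections deal with the same patients.

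**3. Is there a precedence rule?** I found none. Section 5.6 describes its measures as suggested, and Table 3 is titled as guidelines. The mandatory wording in Section 6.1 concerns withholding pembrolizumab, not when steroids start. Neither section refers to the other on steroid timing.

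**4. Is a wait usual in Section 5.6?** These are all the disorders with a Grade 3-4 steroid instruction (infusion reactions in Table 2 not counted):

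| Disorder | Instruction | IV named | Wait |
|---|---|---|---|
| Pneumonitis | "immediately treat with intravenous steroids" | yes | none |
| Diarrhea/colitis | "that persists > 1 week, treat with intravenous steroids followed by high dose oral steroids" | yes | more than 1 week |
| Hypophysitis | "treat with an initial dose of IV corticosteroids followed by oral corticosteroids" | yes | none |
| Hyperthyroidism | "Treat with an initial dose of IV corticosteroid followed by oral corticosteroids" | yes | none |
| Hepatic | IV for 24 to 48 hours | yes | none |
| Renal failure/nephritis | systemic, route not named | no | none |

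A wait appears in 1 of 6 instructions overall, and in 1 of the 5 that name the IV route.

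**The case against.** The best counter-argument is that the two sections can be read together. Table 3 gives no start time, and instruction 3 on its face sets an order, IV before oral, which 5.6 also follows. Table 3 would then supply dose and order, and 5.6 the timing. In addition:

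- The measures in 5.6 are suggested and depend on what the investigator judges necessary. Section 5.5.1 leaves necessary treatment to the investigator, and Section 5.5.2 exempts steroids given for symptoms of suspected immune-related events of clinical interest from its prohibition.
- Pembrolizumab is withheld or stopped under Table 3 regardless of steroid timing, and 5.6 asks for monitoring and fluids.
- Section 5.6 asks that other causes, including infection, be ruled out, and a delay might serve that purpose.
- Being the only disorder with a wait makes the bullet unusual, not wrong.
- The Grade 2 condition has the same mismatch with Table 3, so it is uneven to change only Grade 3-4.

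Some of this stands. Because Table 3 has no start time, no delay in days between the sections can be claimed. Early steroids are permitted, and stopping the drug reduces the risk, although it does not replace steroid treatment.

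The rest does not remove the problem. Reading 5.6 as the source of timing leaves the longer trigger at the higher grade unexplained. The instruction to rule out other causes applies to every disorder, yet no other Grade 3-4 steroid instruction has a wait, and it would not explain a shorter trigger at Grade 2. Both sections are framed as guidance, so that label does not settle precedence. On Grade 2, the documents do not show the three-day condition to be wrong. They do show that it differs from Table 3, and that is for clinicians to resolve.

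**Conclusion.** The concern holds. Section 5.6 conditions IV steroids for Grade 3-4 diarrhea/colitis on more than a week's persistence, 4 days beyond its own Grade 2 trigger. The condition has no counterpart in Table 3 or in the other five Grade 3-4 steroid instructions of 5.6, and no precedence rule exists.

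The consequence is a possible delay in treating severe immune-related colitis. It depends on a site following 5.6 literally and not acting on Table 3. The number of patients affected cannot be estimated from the documents. The two-stage design, the endpoints and the primary analysis are not affected. The change should be made, but it is a safety-wording correction and not a flaw in the statistical plan.

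**What to change.** In Section 5.6, delete the more-than-one-week persistence condition from the Grade 3 or 4 diarrhea/colitis bullet. Add a cross-reference stating that Table 3 in Section 6.1 (the diarrhea/colitis row and general instruction 3) governs steroid treatment of Grade 3-4 diarrhea/colitis. Ask the sponsor's clinicians to reconcile the Grade 2 three-day condition with Table 3's Grade 2 or 3 row.

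The cost is the wording of one bullet and one cross-reference, with no change to sample size, endpoints or analysis.
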